# 9.2.1. Additional TEDDY Clinic Visit after Diagnosis of Type 1 Diabetes in order to Collect Data and Biological Samples at the Final End-point

TEDDY families will be informed that they should contact a TEDDY staff member to arrange an additional TEDDY visit should the TEDDY child develop T1DM in between TEDDY visits. This visit should be organized as soon as possible (within 6 weeks) after the diagnosis of T1DM and include the same ageappropriate procedures as a regular TEDDY visit would (e.g. clinical sample collection, extraction of data from the TEDDY book, administration of TEDDY Study questionnaires), if the 4 year non-HLA genotyping sample has not yet been collected from the child, if possible this sample should also be collected, if possible a 7 time-point MMTT should be completed, if possible a Diabetes Management Form should also be completed and if possible Quality of Life Questionnaires should also be completed. The families will also be asked to collect an additional stool sample as soon as possible (within 7 days) after the diagnosis of T1DM using the standard TEDDY stool sample collection and shipment protocols. An additional stool sample will also be collected within 7 days after the post-diagnosis visit. In August 2018 all stool sample collections were stopped from all subjects.

If diabetes is diagnosed by abnormal glucose values or OGTT results at a routine TEDDY visit an additional visit will be scheduled within 6 weeks of the diagnosis. This additional visit will include the same age-appropriate procedures as a regular TEDDY visit would (e.g. clinical sample collection, extraction of data from the TEDDY book, administration of TEDDY Study questionnaires), if the 4 year non-HLA genotyping sample has not yet been collected from the child, if possible this sample should also be collected, if possible a 7 time-point MMTT should be completed, if possible a Diabetes Management Form should also be completed and if possible Quality of Life Questionnaires should also be completed. The families will be asked to collect an additional stool sample as soon as possible (within 7 days) after the diagnosis of T1DM using the standard TEDDY stool sample collection and shipment protocols and an additional stool sample will also be collected within 7 days after the post-diagnosis visit. In August 2018 all stool sample collections were stopped from all subjects.

This final visit will be the "official" end-point for the child's participation in the TEDDY Study and will offer an opportunity for psychological support to the family.

## **10. Statistical analyses**

The goal of TEDDY is to carry out studies to identify environmental causes of autoantibodies and T1DM in genetically susceptible children. While some environmental exposures can be measured via questionnaires and interviews, other exposures can only be measured via markers in biological samples. We are proposing to do all biomarker tests in a nested case-control fashion. This would be an efficient way to test hypotheses

with regard to dietary and toxin exposures, by only needing to assay a small sample of the entire longitudinal cohort. However, in order for this to be successful, appropriate samples would have to be collected and stored for all visits on all participants (or as indicated).

## 10.1. Master Plan of Analysis

The primary goal of the statistical analyses to be performed as part of this study will be the identification of factors associated with the development of autoimmunity and T1DM. In order to accomplish this, we will employ two different types of analysis, depending on the nature of the factor being studied.

- For those factors whose values will be known to us without additional costs, we will perform log rank tests and Cox Proportional Hazards Regressions. For these analyses, the dependent variable will be the age at which the event being studied (development of autoimmunity or diagnosis of T1DM) occurred. Those not achieving the event when the analyses are being performed and those lost to follow-up without achieving the event will be considered censored as of the date last known to be event-free. The log rank test will be used to study factors with a few discrete values. For example:
  - (a) Family History
  - (b) Haplotype
  - (c) Breast-feeding

For factors with continuous values, we will test for conformity of those values with the proportional hazards assumption by examining the significance of the interaction of the time variable (treated as a time-dependent covariate) with the factor. If there is an indication of a non-zero interaction coefficient, (p < 0.10) we will dichotomize the variable and use the log rank test instead of proportional hazards regression. Otherwise, we will use proportional hazards regression to test for significance at the .01 significance level. The following are examples of factors to be studied in this manner:

- (a) Amounts of certain nutrients consumed
- (b) Duration of breast feeding
- (c) Maternal anxiety and depression as measured by the State Trait Anxiety Inventory and the Edinburgh Postnatal Depression Scale

Proportional hazards regression will be used in both a univariate and multivariate manner and reported both ways. For each factor studied, estimated hazard ratios and their 95% confidence intervals will be computed. When a set of factors that predict conversion to T1DM or autoimmunity are determined as described above, we will compute estimated "survival" curves for subjects having specific factor profiles.

2) For those factors whose determination is costly we will employ a nested casecontrol design. At the time at which a cohort subject converts to autoimmunity or

T1DM (referred to as cases) we will randomly select k subjects who did not convert to autoimmunity or T1DM (controls). The sampling for the selection of matched controls is based upon incidence density sampling which allows the comparison of cases with a subset of the cohort at risk of being cases at the time when each case occurs, or equivalently matches cases and controls for the duration of follow-up. Since controls selected in this way may become cases over time, we will employ over sampling of controls and may select different controls at different points in time.

We will then compare these cases to controls as a matched case control study using conditional logistic regression. The value of k will be determined in order to have at least 80% power based on tables 14 -16, taking into consideration the number of cases available for the analysis. Thus, these expensive determinations will be made only on the cases and their chosen matched controls. Matching will be based on HLA type, study center, duration of follow-up, and completeness of data including serial biological samples. Every effort will be made to use the same controls for multiple case-control studies. This will allow inclusion of all key exposures simultaneously in the analytical model and exploration of confounding, effect modification, and interactions between exposures. The standard set of controls will include only those with complete data/samples for all components of the protocol. Since we do not need to have the same number of controls for each case, we will strive for an average of k controls for each case – not exactly k for each case. These analyses will also be performed in both a univariate and multivariate fashion. Odds ratios for each factor will be computed, as will their 95% confidence intervals. ROC curves for sensitivity vs. 1 specificity based on combinations of these factors will be computed. Here sensitivity refers to the ability of the factors to predict conversion to the study endpoint among those who do convert and specificity refers to ability to predict conversion free survival among those who are.

Similar analyses will be performed for development of autoimmunity and T1DM. Since the cases for T1DM will be a subset of the cases for autoimmunity, we will attempt to use the same controls. However, since there will be fewer cases, additional controls will be needed. Again, the (average) number of controls per case will be guided by tables 14 - 16.

The following is a non-exhaustive listing of planned statistical analyses for the prospective part of the project:

- 1. We will classify infants as to whether or not they had early exposure to cereals or gluten in the diet (vs. those receiving only breast milk for the first 3 months). Those exposed will be compared to those not exposed using the Log Rank Test.
- Subjects will be classified, based on diet questionnaires, as consuming low or high levels of anti-oxidants such as carotenoids, ascorbic acid, and selenium. Those with low levels will be compared to those with high levels with respect to the development of T1DM and autoimmunity using Log Rank Tests.

- 3. Subjects' drinking water will be analyzed and subjects classified as drinking water with high or low concentrations of zinc, and nitrate and as low or high pH. Groups will be compared using the Log Rank Test.
- 4. Cox Regression will be used to study the association of the level of psychosocial stress with the development of T1DM and autoimmunity.

The following analyses will be performed in the nested case control portion of the study:

- The association between the number of enterovirus infections a child has and the development of T1DM and islet autoimmunity will be studied with Cox Regression. Using zero as the reference, dummy variables will be created to represent 1, 2, etc infections. The hazard ratios of these values relative to zero will be estimated and p values of the estimates computed. The same type of analyses will be done for the number of rotavirus infections.
- 2. Low levels of omega-3 fatty acids, EPA, and DHA in children's erythrocyte membranes have been associated with increased risk of islet autoimmunity. The odds ratio for each of these exposures will be estimated.
- 3. Low levels of alpha-tocopherol has been associated with increased risk of islet autoimmunity. The odds ratio for each of this exposure will be estimated

All analyses will be performed using SAS (version 9 or later). Among the procedures to be used will be Proc Logistic, Proc Lifetest, and Proc Phreg, and Proc Lifereg. Observations with missing values of a variable will be omitted from those analyses using that variable, but not from analyses not using those variables. No data imputation methods will be applied to missing values. Programs will be written to check all data for values that are out of range or inconsistent. Reports of such data will be sent to the P.I., discussed, and corrected and the data corrected as appropriate. Indications of confusing data forms or data entry problems will be remediated.

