#### 3.1.6. Washington State

This Clinical Center includes investigators located at the Pacific Northwest Diabetes Research Institute in Seattle. The DEWIT Study, a general population newborn screening effort based on the state-wide newborn screening program in place since 1999, has formed the basis for this center's effort.

*General Population recruitment:* This site plans to screen over five years, about 91,250 neonates from the general population. Recruitment will take place at the obstetrics wards of 18 Puget Sound area hospitals. It is estimated that more than 80% of families approached will consent to screening, resulting in the 91,250 total. About 3.9% will be eligible for intensive follow-up, based on the TEDDY eligibility criteria. We estimate that 37% of families with an infant who screened as eligible will agree to participate.

*First-degree Relatives recruitment:* Over five years, at least 750 infants within the first 3.99 months of life, who are first-degree relatives of patients with T1DM, will be screened. Recruitment is through obstetric departments, pediatricians, and through patients themselves throughout the Pacific Northwest and neighbouring states. A network of collaborating centers will be generated for recruitment of relatives at birth into TEDDY. This center has sampled approximately 1,000 mostly adult T1DM patients over the last 10 years, and actively identifies young children with new T1DM via a general population newborn screening efforts. By expansion of all these efforts, the center expects to screen a total of 750 FDR neonates. Of those, 26.7% are expected to carry one of the ten T1DM high-risk genotypes detailed in the Genetics section below, making them eligible for follow-up. About 75% of FDR families with a neonate deemed high risk after screening are expected to participate.

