## 5. Hypothesis

- 1. Initiation of persistent beta-cell autoimmunity and progression from beta-cell autoimmunity to diabetes is increased with:
  - a. Exposure to a trigger factor during pregnancy, such as infections, preeclampsia, blood incompatibility, or birth weight.
  - b. Differences in the timing of the introduction and/or the type of dietary constituents that include exposure to cereals or gluten, exposure to cow's milk during infancy and/or childhood, and short duration of breast-feeding;
  - c. Lower intake of serum 25 hydroxyvitamin D in early infancy, vitamin E, antioxidants (e.g., carotenoids, ascorbic acid, selenium, or omega-3 fatty acids);
  - d. Higher frequency of specific (e.g., enterovirus, rotavirus, or bacterial) infections, or non-specific childhood infections including those that exhibit molecular mimicry;
  - e. Increased exposure to routine childhood immunizations and their timing;
  - f. Environmental factors that may be contained in drinking water (e.g., low concentrations of zinc or high concentrations of nitrates, or lower pH levels);
  - g. Exposure to household pets, and various allergies;
  - h. Excessive weight gain;
  - i. Increased psychological stress.
- 2. The risk of persistent beta-cell autoimmunity is lower in children from the general population than in offspring or siblings of T1DM patients when stratifying for the HLA DR-DQ genotype and exposure to environmental triggers.
- 3. The interaction of HLA DR-DQ genotype with exposure to dietary or infectious factors leads to increased incidence of beta-cell autoimmunity and T1DM.

4. We expect that in some families study participation will be associated with affective (anxiety, depression) and behavioral responses (e.g. actions to prevent possible T1DM).

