# **6.1.2.** Infants from the general population are eligible for enrollment and long term follow-up if they:

- Have any one of the following HLA genotypes:
  - a. DR4&-DQA1\*030X-DQB1\*0302@ / DR3-DQA1\*0501-DQB1\*0201
  - b. DR4&-DQA1\*030X-DQB1\*0302@ / DR4&-DQA1\*030X-DQB1\*0302@
  - c. DR4&-DQA1\*030X-DQB1\*0302@ / DR8-DQA1\*0401-DQB1\*0402
  - d. DR3-DQA1\*0501-DQB1\*0201 / DR3-DQA1\*0501-DQB1\*0201

@Acceptable alleles in this haplotype include both DQB1\*0302 and \*0304 &For general population subjects, DR4 subtyping must exclude DRB1\*0403

Each extended haplotype listed above must be accurately identified, which usually requires allele typing at two or more of the three genes. For subjects indicated as DR4 above, DR4 subtyping must be used to identify DRB1\*0403 for exclusion. Screening centers may use methods to identify DRB1\*0403 for General Population exclusion which do or do not separately identify DRB1\*0407. TEDDY will allow but not require DRB1\*0407 subjects to be excluded from the General Population follow-up.

• Have a parent or primary caretaker who has given informed consent for surveillance enrollment.

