# **6.1.3.** Infants who are first-degree relatives (FDR) are eligible for enrollment and long-term follow-up if they:

- Have any one of the following HLA genotypes:
  - a. DR4- DQA1\*030X-DQB1\*0302@ / DR3- DQA1\*0501-DQB1\*0201
  - b. DR4- DQA1\*030X-DQB1\*0302@ / DR4- DQA1\*030X-DQB1\*0302@
  - c. DR4- DQA1\*030X-DQB1\*0302@ / DR8- DQA1\*0401-DQB1\*0402
  - d. DR3-DQA1\*0501-DQB1\*0201 / DR3-DQA1\*0501-DQB1\*0201
  - e. DR4- DQA1\*030X-DQB1\*0302@ / DR4- DQA1\*030X-DQB1\*020X
  - f. DR4- DQA1\*030X-DQB1\*0302@ / DR1#- DQA1\*0101-DQB1\*0501
  - g. DR4- DQA1\*030X-DQB1\*0302@ /DR13-DQA1\*0102-DQB1\*0604
  - h. DR4- DQA1\*030X-DQB1\*0302 / DR4- DQA1\*030X-DQB1\*0304
  - i. DR4- DQA1\*030X-DQB1\*0302@ / DR9- DQA1\*030X-DQB1\*0303
  - j. DR3- DQA1\*0501-DQB1\*0201 / DR9- DQA1\*030X-DQB1\*0303

@Acceptable alleles in this haplotype include both DQB1\*0302 and \*0304 #In this DQB1\*0501haplotype, DR10 must be excluded. Only DR1 is eligible

- Each extended haplotype listed above must be accurately identified, which usually requires allele typing at 2 or more of the 3 genes. DR4 subtyping is not required for relatives.
- Have a parent or primary caretaker who has given informed consent for surveillance enrollment.

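### Section 10.1 names log-rank tests for family history and for haplotype without strata, although eligibility admits several genotypes only in relatives, so the pooled tests mix the two factors

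*Protocol*

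**What the plan says.** For factors known without extra cost, section 10.1 states that "we will perform log rank tests and Cox Proportional Hazards Regressions". It then says "The log rank test will be used to study factors with a few discrete values" and lists family history, haplotype and breast-feeding as examples. No strata are named. On adjustment it adds: "Proportional hazards regression will be used in both a univariate and multivariate manner and reported both ways". The covariates are not named. Section 10.6 plans further multivariate models, also without naming family history as a covariate for haplotype.

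Hypothesis 2 in section 5 states that the risk of persistent autoimmunity is lower in general-population children than in offspring or siblings of patients, "when stratifying for the HLA DR-DQ genotype and exposure to environmental triggers".

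Eligibility differs between the two groups. Section 6.1.2 lists four genotypes (a-d) for the general population and excludes DRB1\*0403. Section 6.1.3 lists ten (a-j) for relatives and states that "DR4 subtyping is not required for relatives". A footnote in 6.1.2 ("Acceptable alleles in this haplotype include both" DQB1\*0302 and \*0304) means that item h of the relatives' list already falls under general-population item b. Section 7.1.1 says that relatives have the higher risk even within HLA genotype.

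**The concern.** Carriers of genotypes e, f, g, i and j are all relatives, and so are DRB1\*0403 carriers. The protocol itself says that relatives have higher risk at the same genotype. A log-rank test of haplotype over the whole cohort compares these carriers, all at family-history risk, with a group of a-d carriers made up mainly of general-population children. The difference that it detects is partly or wholly family history.

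In the other direction, a pooled family-history test compares relatives who carry a wider set of genotypes with children who carry a narrower one. That is not the within-genotype comparison of Hypothesis 2. At stake is a false or distorted statement about the relatives-only genotypes, and a crude result standing in for Hypothesis 2.

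**Working it through.** **Inputs from the protocol.** Table 5 and the text below it (section 10.3): 7,013 general-population children at 4% and 788 relatives at 13.3%. Check of the stated case numbers: 7,013 × 0.04 = 280.5 and 788 × 0.133 = 104.8, which match the 281 and 105 given. Section 7.1.3 gives other risks for HLA-eligible children: 1 in 20 (general population) and 1 in 12 (relatives).

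**Assumptions.** The protocol gives neither the share *s* of relatives with a relatives-only genotype nor the risk ratio *r* of those genotypes to a-d among relatives. I take *s* = 0.2 to 0.4, with *r* = 1 (no genotype effect) and *r* = 0.5.

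**Formulas.** Let *g* and *f* be the overall risks in the general population and in relatives.
- Risk of a-d among relatives: x = f / ((1 − s) + s·r)
- Risk of relatives-only genotypes: r·x
- Risk of all a-d carriers pooled: p = (7,013·g + (1 − s)·788·x) / (7,013 + (1 − s)·788)
- Pooled risk ratio: r·x / p, to be compared with the true r

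**One case in full** (g = 0.04, f = 0.133, s = 0.2, r = 0.5): x = 0.133 / 0.9 = 0.1478; r·x = 0.0739; p = (280.5 + 630.4 × 0.1478) / 7,643.4 = 0.0489; ratio = 0.0739 / 0.0489 = 1.51.

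**Pooled ratio, relatives-only genotypes against a-d:**

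| Risks used | True r | s = 0.2 | s = 0.3 | s = 0.4 |
|---|---|---|---|---|
| 4% and 13.3% | 1 | 2.79 | 2.84 | 2.90 |
| 4% and 13.3% | 0.5 | 1.51 | 1.61 | 1.73 |
| 1 in 20 and 1 in 12 | 1 | 1.58 | 1.59 | 1.60 |
| 1 in 20 and 1 in 12 | 0.5 | 0.87 | 0.92 | 0.97 |

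**Family history.** The pooled ratio is 0.133 / 0.04 = 3.3. Within a-d it is x / 0.04. At r = 0.5 this is 3.7 (s = 0.2), 3.9 (s = 0.3) and 4.2 (s = 0.4). At r = 1 it equals the pooled 3.3.

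**Contrasts among a-d.** Relatives are at most 788 / 7,801 = 10% of these children, and no a-d genotype is closed to either group, so the distortion is far smaller.

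**Behaviour of the test.** I used 1,000 simulated cohorts with exponential hazards, 15 years, no loss to follow-up, risks of 4% and 13.3%, s = 0.3 and two-sided alpha 0.01. Here the true effect is a hazard ratio.
- True ratio 1: the unstratified log-rank test was significant in 99% of runs. Stratified by FDR status, it was significant in about 1%.
- True ratio 0.5: the unstratified test was significant in the wrong direction in 40% of runs and in the right direction in none. The stratified test was significant in the right direction in 62% and in the wrong direction in none.

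**The case against.** The strongest reply is that the protocol never says the tests are unstratified. Section 10.1 gives examples, strata are often left to a statistical analysis plan, and one may exist. Cox regression, univariate and multivariate, is planned for the same factors, and Hypothesis 2 already states the HLA stratification. No section names the log-rank test as the test of Hypothesis 2, and no section plans a contrast of relatives-only genotypes against a-d. The primary objective concerns environmental factors, and the nested case-control studies match on HLA.

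Much of this stands. A reader might infer that the plan fixes a crude analysis as the only or final one, or that Hypothesis 2 will go untested. The text supports neither. What remains is a mismatch inside the protocol: section 5 states a stratified comparison, and section 10.1 names a test for the same factor without it. The multivariate Cox model closes the gap only in part. Its covariates are not named, family history is nowhere named as an adjuster for haplotype, and the univariate result is to be reported as well.

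A reader might also count six relatives-only genotypes from items e-j. Item h is covered by general-population item b through the allele footnote, so there are five, with DRB1\*0403 carriers as a further relatives-only group.

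**Conclusion.** The concern holds in a limited form. As written, the haplotype test in section 10.1 confounds relatives-only genotypes with family history. This does not depend on any assumed genotype effect: with none, the pooled ratio is about 2.8-2.9 at the planning risks and about 1.6 at the counselling risks, for shares of 20-40%.

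It is tempting to conclude that the haplotype result will point the wrong way. That does not follow in general. With an assumed true ratio of 0.5, the pooled ratio is reversed (1.5-1.7) at 4% and 13.3%, but only attenuated (0.87-0.97) at 1 in 20 and 1 in 12. Reversal depends on the assumed share, the assumed effect and the choice between the protocol's two sets of risks. It also concerns only relatives-only genotypes against a-d.

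The family-history result does not reverse. It is diluted, at 3.3 against 3.7-4.2, if the extra genotypes carry half the risk, and unbiased from this source if they carry the same risk.

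**What to change.** Amend section 10.1 as follows.

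1. Stratify the haplotype or genotype analysis (log-rank or Cox) by FDR status, and report relatives-only genotypes within relatives only.
2. Stratify the family-history test by HLA genotype, restricted to genotypes eligible in both groups. Handle DRB1\*0403 carriers alike in both groups; restricting to a-d alone would leave them among the relatives only. The high-resolution DRB1, DQA1 and DQB1 typing planned in section 7.1.2 for enrolled children makes this possible.
3. Name the test in item 2 as the test of Hypothesis 2.

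This needs a strata specification for each analysis and no new data. The cost is precision: estimates for relatives-only genotypes will rest on the 788 planned relatives alone, which is all the information that the design holds on them free of family history.

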Ov	er 5 years	General Population	on FDF	ł			
Enroll		7,013	788				
Cases - autoantibodies by age 6		281 (4%)	105 (13.	3%)			
Cases - T1DM by age 15		281 (4%)	105 (13.	3%)			

Based on submissions by the participating institutions, we expect to be able to enroll 7,013 subjects from the general population and 788 relatives in five years. Those from the general population and the relatives are expected to have about 4% and 13.3% autoimmune conversion at 6 years respectively. Tables 6-13 below give the power for a Log Rank Test at a two-sided 0.01 significance level for the general population subjects, the relatives, and the pooled sample accrued over 5 years with 15 years of post-accrual follow-up for dichotomous pre-birth triggers of frequencies 1%, 5%, 10%, and 20% and hazard ratios of 1.5 and 2.0 and losses to follow-up at rates of 0%, 2%, 5%, and 10% per year. These calculations are based on the method of Lakatos (Lakatos, 1998) using a computer program described by Cantor (Cantor, 2003).

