## Table 6: Power for Prospective Study- General Population –Diabetes End Point, Alpha = .01, N = 7013, 5 Years Accrual, Follow-Up to age 15, 4% Conversion among Unexposed at 15 Years

Exposed %	LTFU %/year	Power ( HR = 1.5)	Power ( HR = 2.0 )
1	0	0.05	0.21
5	0	0.26	0.89
10	0	0.52	0.99
20	0	0.81	0.99
1	2	0.04	0.17
5	2	0.21	0.82
10	2	0.44	0.98
20	2	0.72	0.99
1	5	0.03	0.13
5	5	0.16	0.71
10	5	0.34	0.95
20	5	0.59	0.99
1	10	0.03	0.09
10	10	0.23	0.83
20	10	0.42	0.98
5 10	10 10	0.11 0.23	0.52 0.83

Table 7: Power for Prospective Study- Relatives – Diabetes End Point Alpha = .01, N = 788, 5 Years Accrual, Follow-Up to age 15, 13.3% Conversion among Unexposed at 15 Years

Exposed %	LTFU %/year	Power (HR = 1.5)	Power ( HR = 2.0)
1	0	0.02	0.06
5	0	0.07	0.33
10	0	0.14	0.62
20	0	0.27	0.87
1	2	0.02	0.05
5	2	0.06	0.27
10	2	0.12	0.53
20	2	0.22	0.80
1	5	0.02	0.04
5	5	0.05	0.21
10	5	0.09	0.42
20	5	0.17	0.68
1	10	0.02	0.03
5			0.03
	10	0.04	
10	10	0.06	0.29
20	10	0.11	0.51

Table 8: Power for Prospective Study- Pooled Sample – Diabetes End Point,
Alpha = $.01$ , N = 7801, 5 Years Accrual, Follow-Up to age 15,
5.5% Conversion among Unexposed at 15 Years

$\begin{array}{c ccccccccccccccccccccccccccccccccccc$	Exposed %	LTFU %/year	Power ( HR = 1.5)	Power ( HR = 2.0 )
$ \begin{array}{c ccccccccccccccccccccccccccccccccccc$				
$\begin{array}{c ccccccccccccccccccccccccccccccccccc$	1	0	0.07	0.35
$\begin{array}{c ccccccccccccccccccccccccccccccccccc$	5	0	0.43	0.98
$\begin{array}{c ccccccccccccccccccccccccccccccccccc$	10	0	0.75	0.99
$ \begin{array}{cccccccccccccccccccccccccccccccccccc$	20	0	0.95	0.99
$\begin{array}{c ccccccccccccccccccccccccccccccccccc$	1	2	0.06	0.29
$\begin{array}{c ccccccccccccccccccccccccccccccccccc$	5	2	0.35	0.96
$\begin{array}{c ccccccccccccccccccccccccccccccccccc$	10	2	0.66	0.99
$ \begin{array}{cccccccccccccccccccccccccccccccccccc$	20	2	0.91	0.99
$ \begin{array}{cccccccccccccccccccccccccccccccccccc$				
$\begin{array}{cccccccccccccccccccccccccccccccccccc$		5	0.05	0.22
20         5         0.82         0.99           1         10         0.04         0.14           5         10         0.18         0.75           10         10         0.37         0.96	5	5	0.27	0.90
1         10         0.04         0.14           5         10         0.18         0.75           10         10         0.37         0.96	10		0.54	0.99
5100.180.7510100.370.96	20	5	0.82	0.99

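### When proportional hazards is rejected, dichotomising the factor and switching to the log-rank test does not address the non-proportionality, and costs about a third or more of the information

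*Protocol*

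**What the plan says.** Protocol section 10.1 (Master Plan of Analysis) treats factors known without added cost prospectively, using log-rank tests and Cox regression. For a continuous factor it adds an interaction between the factor and time. If that interaction reaches p < 0.10, "we will dichotomize the variable and use the log rank test instead of proportional hazards regression". If it does not, "Otherwise, we will use proportional hazards regression to test for significance at the .01 significance level". The examples given for this route are nutrient intakes, breast-feeding duration, and maternal anxiety and depression scores.

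The same section says Cox regression will be reported both univariately and multivariately, and promises: "For each factor studied, estimated hazard ratios and their 95% confidence intervals will be computed".

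Models with time-dependent covariates appear in section 10.6, in the context of gene-environment interactions. They are not tied to a factor flagged under 10.1.

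**The concern.** The rule detects that a factor's hazard ratio changes with age and then moves to a test that is most efficient when the ratio does not change. Cutting the factor in two does not make its hazards proportional. It discards the ordering within each half, and the change with age is neither modelled nor reported.

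This matters because several hypotheses in sections 5 and 8.12.5 concern timing: age at dietary introduction, vitamin D in early infancy, the onset of puberty. Age-varying effects are therefore plausible. For a flagged factor the log-rank test gives a p-value but no hazard ratio and no covariate-adjusted result, and in an unrandomised cohort adjustment for confounders is needed.

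**Working it through.** **1. The plan's own figure.** Section 10.3 says its tables "give the power for a Log Rank Test at a two-sided 0.01 significance level". The inputs are "7,013 subjects from the general population and 788 relatives in five years" and, for Table 6, "4% Conversion among Unexposed at 15 Years". Take the Table 6 cell with 20% exposed, hazard ratio 1.5 and no loss to follow-up.

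- Hazard in the unexposed: −ln(0.96)/15 = 0.00272 per year.
- Five years of accrual plus 15 years after it gives a mean follow-up of 17.5 years.
- Events: 7,013 × [0.8 × 0.0465 + 0.2 × 0.0690] ≈ 358.
- Freedman's formula with allocation ratio r = 0.25: √(358 × 0.25) × 0.5/(1 + 0.25 × 1.5) − 2.576 = 0.864, so power is 0.806.
- A Lakatos-type calculation gives 0.803. The stated value is 0.81, so the figure is reproduced. (With exactly 15 years for every child it would be 0.73; that is a separate matter.)

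This power is for a binary factor with a constant hazard ratio. It does not carry over to a continuous factor flagged as non-proportional.

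**2. Information kept by dichotomising.** For a normal factor with the top fraction q split off at c, the efficiency relative to the linear score is φ(c)²/[q(1 − q)]. At the median this is 2/π = 0.637. Starting from power 0.80 at two-sided 0.01: (2.576 + 0.842) × √0.637 − 2.576 = 0.152, which is power 0.56.

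| Cut | Information kept | Power (from 0.80) |
|---|---|---|
| Median | 64% | 0.56 |
| Top third | 59% | 0.52 |
| Top quarter | 54% | 0.47 |
| Top 20% | 49% | 0.43 |
| Top 10% | 34% | 0.28 |

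**3. Simulation of the planned rule.** Inputs from the protocol: the pooled 7,801 children and "5.5% Conversion among Unexposed at 15 Years" (Table 8), giving about 435 events; alpha 0.01. Assumptions: normal factor, median cut, 15-year follow-up, hazard ratio changing at age 6, and the log hazard ratios per SD shown below. There were 2,000 runs per pattern.

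| Log HR before / after age 6 | Flagged | Continuous Cox | Planned rule | Joint 2-df test, all factors |
|---|---|---|---|---|
| 0.26 / 0 (early only) | 74% | 0.38 | 0.25 | 0.64 |
| 0.30 / 0.08 (declining) | 61% | 0.83 | 0.69 | 0.89 |
| 0.30 / −0.20 (reversing) | 99.8% | 0.012 | 0.009 | 0.93 |
| 0.165 / 0.165 (proportional) | 10.5% | 0.82 | 0.80 | 0.73 |

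Among flagged runs only, continuous Cox against log-rank was 0.38 against 0.21 (early only) and 0.82 against 0.59 (declining). After dichotomising, the factor still failed the same p < 0.10 check in 73%, 71% and 96% of flagged runs for the first three patterns. A separate set of runs gave the same ordering: about 0.22 for the rule against 0.34 for Cox (early only), and 0.65 against 0.82 (declining).

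**4. Type I error.** Under the null (6,000 runs) the rate was 0.008 for the log-rank test, 0.009 for the planned rule and 0.011 for the joint test applied to all factors.

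The joint test behaves differently if it is applied only to flagged factors while the rest keep the 1-df Cox test. It then rejects in 0.067 of flagged null factors, because flagging has already selected large interactions. Overall: 0.9 × 0.01 + 0.1 × 0.067 = 0.0157. A simulation of 30,000 null cohorts gave 0.0155 overall and 0.070 among flagged factors, against 0.0098 for the unconditional joint test.

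**The case against.** The strongest defence is that the log-rank test is a valid test of no association whether or not hazards are proportional. That stands: with a pre-set cut its error rate is held. The study also calls itself hypothesis-forming, and a blunt fallback in such a study is a matter of efficiency.

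The scope is limited too. Viral, bacterial, inflammatory and dietary-biomarker exposures go to the nested case-control analysis (section 10.5.1). Antioxidant intake and drinking water are already planned as low/high log-rank comparisons in 10.1, so the rule changes nothing for them.

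The promise of a hazard ratio for each factor could mean that Cox estimates will be produced anyway. If so, the section conflicts with its own wording that the log-rank test is used in place of Cox regression, and the estimate would be an average over ages whose constancy had just been rejected.

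A reader might infer more than the protocol supports:

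- **That most of the power is lost.** At a median cut it falls from 0.80 to 0.56. More than half is lost only when roughly the top 10-15% or fewer are split off, and the protocol names no such cut.
- **That dichotomising causes the near-total loss for a reversing effect.** Plain continuous Cox fails there as well (0.012). The fault is not modelling the interaction.
- **That being triggered for about 10% of truly proportional factors is a defect.** That is simply the size of the p < 0.10 check.
- **That the missing cut-point is an omission.** It may be fixed in a statistical analysis plan that is not at hand.

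**Conclusion.** The point holds as a flaw of efficiency and reporting, not of validity. The fallback does not address the non-proportionality that triggers it. It keeps about 64% of the information at a median cut and less elsewhere, and it loses to the Cox test it replaces by roughly 0.12 to 0.17 in power across the early-only and declining patterns. It also leaves a flagged factor without the hazard ratio and multivariate estimate promised in section 10.1.

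The 64% figure assumes a normally distributed factor with a linear effect on the log hazard. The simulated powers rest on assumed effect sizes and a change at age 6. Their ordering is the finding; the exact values are illustrative. The conclusion covers only continuous factors in the prospective analysis.

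**What to change.** In section 10.1, delete the dichotomise-and-log-rank rule and keep each such factor continuous in Cox regression. Then:

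- Test every continuous factor once, at 0.01, with a pre-specified joint 2-df test that does not depend on the interaction p-value. The two terms can be the factor in two pre-set age periods, or the factor plus its interaction with time.
- Use the p < 0.10 check only to decide whether age-period-specific hazard ratios with 95% confidence intervals are reported, univariately and multivariately.
- Do not reserve the joint test for flagged factors, since that raises type I error to about 0.016 overall.
- Fix the age boundary in advance. Age 4, where the visit schedule changes, is one option; it was not the boundary simulated, and a boundary far from the real change would gain less.

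The cost is wording and a few lines of code, with no new data; time-dependent terms are already foreseen in section 10.6. The price is one extra degree of freedom: power of about 0.71-0.73 instead of 0.78-0.80 when hazards are truly proportional.
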